### **7.0 STRATEGIES FOR RECRUITMENT**

Subjects will be recruited from the Structural Heart Disease clinical programs of the participating hospitals.

The distribution of planned enrolling sites assures accessibility of the trial to ethnically, racially, and economically diverse populations. The study will track sex, age, ethnicity, and racial background of subjects.

Once recruited, subject retention rate is expected to be high because follow-up activities are not onerous and are timed to correspond with routine follow-up medical care, without prohibitively expensive follow-up testing.

## 8.0 SAMPLE COLLECTION, STORAGE AND TRACKING PLAN

Imaging data (such as from angiography, fluoroscopy, CT, and echocardiography) constitute the only information to be collected. CT examinations performed for clinical evaluation prior to signing informed consent may be used as the baseline scan.

CT and fluoroscopy data will be analyzed at the NHLBI DIR Core Laboratory. These data will be transmitted on electronic media such as a DVD via carrier or using secure file transfer mechanisms abiding Federal Information Security Management Act (FISMA), Health Insurance Portability and Accountability Act of 1996 (HIPAA) and local institutional standards (such as <https://dirweb.nhlbi.nih.gov/oc>).

Imaging data are transmitted to a central facility (NHLBI) using secure HIPAA compliant methods and are stored in a secure Picture Archive Computer System (PACS), according to local institutional standards. This includes imaging data used for screening eligibility.

Necropsy specimens will be handled according to local institutional medical standards and will be disposed accordingly.

### 8.1 DATA TRANSFER TO COLLABORATORS

De-identified and de-linked data and images will be posted at the NHLBI Cardiovascular Intervention Structural Heart Image Data Repository (<https://[name].nhlbi.nih.gov/repository/index.htm> or equivalent). They are provided for the purpose of medical education and research. Data are de-identified and de-linked, so that patients can not readily be identified, and are therefore not considered human research subjects research data under US 45CFR§46.104(d)(2)(i).

De-identified images will also be transferred to collaborating investigators at academic and industry sites. They are provided for the purpose of medical education and research. For some, data are de-identified and de-linked, so that patients can not readily be identified, and are therefore not considered human research subjects research data under US 45CFR§46.104(d)(2)(i). For others, data are de-identified but linked, in case receiving collaborators require additional information. The table below indicates which recipients will receive de-identified but linkable data and which will only receive de-identified and de-linked data.

These recipients include all site Principal Investigators and:

| Recipient              | Organization                    | Location                 | Linkable  |
|------------------------|---------------------------------|--------------------------|-----------|
| [name]          | Transmural Systems              | Andover, MA, USA         | Linked    |
| [name], MD | Pusan National University       | Busan, Republic of Korea | Linked    |
| [name]   | Georgia Institute of Technology | Atlanta, Georgia, USA    | De-linked |
| [name]   | 3mensio Pie Medical Esaote      | Bilthoven, Netherlands   | De-linked |

## 9.0 BIOSTATISTICAL AND ANALYTICAL CONSIDERATIONS

### 9.1 SAMPLE SIZE

This is an early feasibility study of a device not previously used in humans. An arbitrary initial sample size of 30 is proposed in coordination with the FDA Centers for Devices and Radiologic Health, which is increased from 15 in Amendment A

Up to 60 subjects will be consented until 30 subjects undergo attempted Transcatheter Mitral Cerclage Annuloplasty total in this protocol.

We will adhere to the extent possible to consensus guidelines that have been established for the analysis and reporting of transcatheter mitral valve repair investigational procedures (MVARC).

There are no prespecified acceptance criteria for failure rate.

## 9.2 STUDY ANALYSIS

Analyses will be performed using principles both of (1) intention-to-treat, defined as attempting or initiating Transcatheter Mitral Cerclage Annuloplasty, and (2) as-treated, defined as completing Transcatheter Mitral Cerclage Annuloplasty. We expect these to be the same.

Clinical events are classified by the site Principal Investigator and confirmed by the NIH Principal Investigator. The results of the study will be released within 12 months of study completion.

The study will be analyzed using descriptive statistics, including a case-by-case narrative summary of major adverse events. Representative descriptive statistics include typical demographic features (age, sex, comorbidity), symptoms (NYHA heart failure classification), ventricular geometry and function (volumes, ejection fraction), hemodynamics (chamber pressures), procedure characteristics (procedure time, contrast exposure), etc.

We will attempt to stratify subjects by various phenotypes (HFrEF vs HFpEF, MR severity, dimensions) and associate these with measurements (cerclage geometric shortening), and outcomes (symptom status, functional status, change in chamber volumes and regurgitation, adverse events), as allowed by the small sample size.

Afterwards, we will survey for parameters associated with an increased risk of major adverse events.

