| Blood tests (see below)   |                       | X                     |             | X         | X X X          |                        |                           |                |                |                |
| Vital signs and in-person visit   |                       | X                     |             |           | X X X          |                        |                           |                |                |                |
| Cardiac CT contrast-enhanced gated dynamic (Baseline may be up to 6 months old) | Screening or baseline | Screening or baseline | Inpatient * | 30-90d*   | X X            |                        |                           |                |                |                |
| Transesophageal echocardiogram. May be omitted day 0 with SEC concurrence       | Screening or baseline | Screening or baseline | X           |           |                |                        |                           |                |                |                |
| Transcatheter Mitral Cerclage Annuloplasty                                      |                       |                       | X           |           |                |                        |                           |                |                |                |
| Transthoracic echocardiogram (TTE). Baseline may be up to 3 months old.         | Screening or baseline | Screening or baseline |             | X X X X X |                |                        |                           |                |                |                |
| ECG   |                       | X                     |             | X X X X X |                |                        |                           |                |                |                |
| Adverse event assessment  |                       |                       | X X         | X X X X X |                |                        |                           |                |                |                |

|  | Screening ± 6 wks | Baseline ± 6 wks | Day 0 | Inpatient | 30 d (±14d) FU | 6 mo (± 1 mo) (range) FU | 12 mo (± 1 mo) (range) FU | 2 yrs (± 1 mo) (range) | 3 yrs (± 1 mo) | 4 yrs (± 1 mo) | 5 yrs (± 1 mo) |
|--|-------------------|------------------|-------|-----------|----------------|--------------------------|---------------------------|------------------------|----------------|----------------|----------------|

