## 9.5 EXPLORATORY ENDPOINTS

Exploratory endpoints include:

- MVARC 30-day Device Success
- MVARC 1-year Patient Success
- Change from baseline in degree of mitral regurgitation post-procedure, at 30 days, 6-months, and 12-months
- Change from baseline in left ventricular dimensions/volumes post-procedure, at 30 days, 6-months, and 12-months
- Change in symptoms assessed by New York Heart Association heart failure classification and by Kansas City Cardiomyopathy Questionnaire
- Mortality, all-cause, cardiovascular vs non-cardiovascular, peri- vs non-periprocedural, including Transcatheter Mitral Cerclage Annuloplasty relatedness)
- Neurological events as reported by the site clinicians only
- Procedural Myocardial infarction
- VARC-2 vascular complications
- MVARC bleeding complications, which includes pericardial bleeding
- AKI acute kidney injury
- Arrhythmia and conduction disturbances
- Infection related to the cerclage
- Device related technical failure: Device Failure, Pericardial effusion, Conversion to open surgery, Device mal-positioning or migration or detachment, Device fracture, Unintended damage to native mitral valve or tricuspid valve apparatus
- Device thrombosis

- Change in optional exercise endpoints including mitral regurgitation severity, pulmonary artery pressure estimated from tricuspid regurgitation jet velocity, and gas exchange, when available.

Procedural myocardial infarction will rely on the updated Fourth Universal Definition Type II (supply-demand mismatch) within 48 hours of cerclage. This definition most closely applies to the presumed etiology of myocardial infarction theoretically attributable to cerclage. Application of this definition requires rise and fall of cardiac troponin above the 99th upper limit of normal, combined with any of: symptoms of acute myocardial ischemia; new ischemic ECG changes; development of pathologic Q waves, imaging evidence of new loss of viable myocardium or new regional wall motion abnormality in a pattern consistent with an ischemic etiology .

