## 9.7 CORE LABORATORIES

The NHLBI CT and Echocardiography Core Laboratories will analyze all imaging and compare post-procedure imaging with baseline (pre-procedure) imaging. Analysis will include but will not be limited to the following:

- Assessment of baseline eligibility
  - Likelihood of entrapment of Cardiac Implanted Electronic Devices (CIED) by the cerclage system
  - Suitability of coronary venous anatomy for the cerclage procedure
  - Geometry of likely cerclage trajectory
- Assessment of cerclage device post-implantation characteristics
  - Cerclage position
  - Cerclage integrity
  - Cerclage-related compression of underlying coronary arteries
  - Cerclage-related tricuspid valve dysfunction
- Assessment of impact of cerclage on heart function
  - Cardiac chamber size and function
  - Severity of mitral valve regurgitation
  - Impact of cerclage on function of non-target valve function (tricuspid and aortic)

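### Section 9.2 relates MR severity and chamber dimensions to their own change from baseline; for these two pairings, measurement error alone favours the leakier and larger hearts.

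*Combined protocol and SAP*

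**What the plan says.** Section 9.2 (Study analysis) says: "We will attempt to stratify subjects by various phenotypes (HFrEF vs HFpEF, MR severity, dimensions) and associate these with measurements". It goes on to name the "outcomes (symptom status, functional status, change in chamber volumes and regurgitation, adverse events), as allowed by the small sample size".

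Section 9.5 (Exploratory endpoints) defines the two relevant outcomes. The entry for the leak reads "Change from baseline in degree of mitral regurgitation post-procedure, at 30 days, 6-months, and 12-months". Ventricular size has its own entry, worded in the same way and over the same visits: "Change from baseline in left ventricular dimensions/volumes post-procedure, at 30 days, 6-months, and 12-months".

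Section 9.7 (Core laboratories) has the core laboratories "compare post-procedure imaging with baseline (pre-procedure) imaging".

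The schedule in section 5.4 places the pre-procedure TTE and CT at screening or baseline, with no planned repeat of either before the procedure: "Transthoracic echocardiogram (TTE). Baseline may be up to 3 months old" and "Cardiac CT contrast-enhanced gated dynamic (Baseline may be up to 6 months old". TEE is also scheduled at screening or baseline.

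Section 5.1 describes an open-label study and no comparator. Section 9.1 sets the size at 30 attempted procedures. Section 9.2 calls the analysis descriptive and specifies no test, model, cut-point or significance level for the stratified work. The plan does not mention regression to the mean, repeat baseline readings or measurement repeatability.

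**The concern.** Two of the possible pairings put one measurement on both sides: MR severity against change in regurgitation, and dimensions against change in chamber volumes. Change is follow-up minus baseline. A baseline reading that is too high by chance therefore pushes the subject into the upper stratum and also enlarges the apparent fall. The reverse happens to a reading that is too low. The result is a gap between strata in a fixed direction, with no difference in true response behind it. Using continuous predictors in place of strata does not remove it.

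What is at stake is the descriptive account of which hearts show the most reduction in leak or volume. With no untreated group, the artefact can be neither seen nor subtracted.

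**Working it through.** **Inputs.** N = 30 (section 9.1). The stratifier and the change are paired as above (sections 9.2 and 9.5). The reliability R of a single reading, meaning the share of its between-subject variance that is true, is not in the documents. It is an assumption, shown over a range. The plan gives no figure for this analysis, so there is nothing of its own to reproduce.

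**Model.** Scale the observed baseline to SD 1. Baseline = T + e1, follow-up = T + e2 − constant, with Var(T) = R, Var(e1) = Var(e2) = 1 − R, and independent errors. The device effect is the same constant for everyone, so the true gap between strata is zero.

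**Closed form.** Change = e2 − e1 − constant.
- Cov(baseline, change) = −(1 − R). This is also the slope, because the baseline variance is 1.
- Var(change) = 2(1 − R).
- Correlation = −(1 − R)/√(2(1 − R)) = −√((1 − R)/2).

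For a median split of 30 normal values, the two halves differ in mean observed baseline by about 1.556 SD (simulated). The spurious gap in change is therefore about (1 − R) × 1.556.

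| R | correlation | gap in change, baseline SD | studies in which the upper half looks better |
|---|---|---|---|
| 0.50 | −√0.25 = −0.50 | 0.50 × 1.556 = 0.78 | about 99% |
| 0.70 | −√0.15 = −0.39 | 0.30 × 1.556 = 0.47 | about 96% |
| 0.90 | −√0.05 = −0.22 | 0.10 × 1.556 = 0.16 | about 83% |
| 0.95 | −√0.025 = −0.16 | 0.05 × 1.556 = 0.08 | about 75% |
| 0.98 | −√0.01 = −0.10 | 0.02 × 1.556 = 0.03 | about 66% |

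The last column comes from simulated studies of 30 subjects; without bias it would be 50%. As a yardstick only, a two-sided 5% test of the correlation would reject in about 83%, 57%, 22%, 13% and 8% of studies.

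**Remedy 1: strata from a separate baseline reading.** If its error is independent of the reading subtracted in the change, the gap is 0.00 SD and the upper half looks better in about 50% of studies, at every R tried. If half the error variance is shared by the two readings (assumption, for example a passing loading state), half the bias stays: (1 − R)/2 × 1.556, which is 0.23 SD at R = 0.7 and 0.08 SD at R = 0.9.

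**Remedy 2: change against the mean of baseline and follow-up (Oldham).** Covariance = (Var(follow-up) − Var(baseline))/2. This is zero if response is uniform. If true response varies with SD 0.5 independently of baseline, it is 0.25/2 = 0.125. At R = 0.9, Var(change) = 2 × 0.1 + 0.25 = 0.45 and Var(mean) = 0.9 + 0.25/4 + 0.1/2 = 1.0125, so r = 0.125/√(0.45 × 1.0125) = +0.19. The simulation gave +0.14 to +0.20 for R from 0.7 to 0.95, with 11% to 20% rejections at a nominal 5%. The sign is opposite: larger hearts would seem to improve less.

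**The case against.** - **The self-pairing is inferred.** Section 9.2 lists phenotypes and outcomes without matching them, does not use the word baseline, and names no modality. With CT, TEE and TTE all scheduled before the procedure, an uncoupled analysis is compatible with the text. This stands as a limit on the wording. It does not remove the point: phenotypes used to stratify are naturally pre-treatment values, section 9.5 measures change from baseline, and nothing in the plan keeps the two readings apart.
- **The analysis is descriptive and hedged.** A reader might infer that the plan, followed as written, yields false significance far above 5%. The documents do not support that, because no test or significance level is specified. The relevant quantity is the bias in the stratum gap. The hedges about attempting the work and about small numbers concern precision, so they do not answer a bias.
- **The stakes can be overstated.** A reader might infer that this analysis will choose the population to carry forward. No section says so. The one change of population on record, Amendment F, rested on symptomatic and functional benefit out of proportion to MR reduction (section 6.3), and those outcomes are not coupled in this way.
- **Reliability may be high.** Entry after Amendment F runs from mild MR upward, and a wide true spread raises R. At 0.95 or above the gap is small. This stands.
- **Remedies are imperfect.** It is tempting to say that either remedy restores a clean comparison. The working shows otherwise: Oldham fails if true response varies, and a second modality fails in part if errors are shared. MR recorded as an ordinal grade also does not fit Oldham or this normal model directly.

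**Conclusion.** The point holds as a bias in two exploratory associations: MR severity with change in regurgitation, and dimensions with change in chamber volumes. For any reliability below 1 the expected direction is fixed, toward greater apparent improvement in the leakier or larger stratum. The size depends on a reliability that the documents do not give. With 30 subjects and a median split, the gap runs from about 0.78 baseline SD at 0.5 to 0.08 at 0.95, assuming equal independent errors before and after and a uniform device effect.

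A reader might infer that the largest and leakiest hearts are bound to look like the best responders. That is too strong for a single study: the upper half looks better in about 99% of studies at reliability 0.5 but about 66% at 0.98.

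Symptom status, functional status, adverse events, technical success and procedural success are not affected in this way. This is an inexpensive improvement to an exploratory analysis and does not bear on the study's main conclusions.

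**What to change.** Add one paragraph to section 9.2, limited to these two associations:

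1. Form the strata from a scheduled baseline measurement that is not the reference for the change. For example, use baseline CT for chamber size and baseline TEE for MR severity, and take the change from core-laboratory TTE. Prefer readings from different days, which the screening and baseline windows in section 5.4 allow.
2. State that a raw association of a baseline value with its own change will not be read as evidence of who responds.
3. If Oldham's method is used, label it a sensitivity analysis, restrict it to continuous measures, and note that it is biased the other way when true response varies between subjects.

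Cost: a paragraph and a little extra analysis, with no new visits or scans. The downside is that a second modality is a noisier stratifier, so real differences in response become harder to see. It also does not remove error common to both modalities; about half the bias remains if half the error variance is shared.

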## 9.3 PRIMARY ENDPOINT: TECHNICAL SUCCESS

The primary endpoint is **Technical success**. This endpoint is measured at exit from the catheterization laboratory. All of the following must be present:

- Alive
- Successful deployment and correct final positioning of a single intended Transcatheter Mitral Cerclage Annuloplasty. Repositioning and recapture of the device, if needed, is not classified as failure.
- Retrieval of the cerclage delivery system
- Absence of cerclage-related coronary artery compression and absence of additional procedure such as percutaneous coronary intervention (PCI) to relieve coronary artery compression
- No additional unplanned or emergency surgery or re-intervention related to the cerclage or delivery system

The primary endpoint is classified by the NHLBI Principal Investigator and reviewed for possible reclassification by the Clinical Events Adjudication Committee.

## 9.4 SECONDARY ENDPOINTS

### 9.4.1 Procedural success

The secondary endpoint is **Procedural success**. This endpoint is measured at 30 days. All of the following must be present

- Technical success
- No cerclage device-related Serious Adverse Device Effects, defined as VARC-2 life-threatening bleeding, major vascular or cardiac complications related to the cerclage requiring unplanned reintervention or surgery

Such reinterventions are directly related to the valve. Pacemaker implantation, for example, is consistent with procedural success.

The secondary endpoint is classified by the NHLBI Principal Investigator and reviewed for possible reclassification by the Clinical Events Adjudication Committee.

## 9.5 EXPLORATORY ENDPOINTS

Exploratory endpoints include:

- MVARC 30-day Device Success
- MVARC 1-year Patient Success
- Change from baseline in degree of mitral regurgitation post-procedure, at 30 days, 6-months, and 12-months
- Change from baseline in left ventricular dimensions/volumes post-procedure, at 30 days, 6-months, and 12-months
- Change in symptoms assessed by New York Heart Association heart failure classification and by Kansas City Cardiomyopathy Questionnaire
- Mortality, all-cause, cardiovascular vs non-cardiovascular, peri- vs non-periprocedural, including Transcatheter Mitral Cerclage Annuloplasty relatedness)
- Neurological events as reported by the site clinicians only
- Procedural Myocardial infarction
- VARC-2 vascular complications
- MVARC bleeding complications, which includes pericardial bleeding
- AKI acute kidney injury
- Arrhythmia and conduction disturbances
- Infection related to the cerclage
- Device related technical failure: Device Failure, Pericardial effusion, Conversion to open surgery, Device mal-positioning or migration or detachment, Device fracture, Unintended damage to native mitral valve or tricuspid valve apparatus
- Device thrombosis

- Change in optional exercise endpoints including mitral regurgitation severity, pulmonary artery pressure estimated from tricuspid regurgitation jet velocity, and gas exchange, when available.

Procedural myocardial infarction will rely on the updated Fourth Universal Definition Type II (supply-demand mismatch) within 48 hours of cerclage. This definition most closely applies to the presumed etiology of myocardial infarction theoretically attributable to cerclage. Application of this definition requires rise and fall of cardiac troponin above the 99th upper limit of normal, combined with any of: symptoms of acute myocardial ischemia; new ischemic ECG changes; development of pathologic Q waves, imaging evidence of new loss of viable myocardium or new regional wall motion abnormality in a pattern consistent with an ischemic etiology .

## 9.6 INDEPENDENT CLINICAL EVENTS ADJUDICATION

An independent Clinical Events Adjudication Committee will review all of the following that occur in the first year:

- Deaths
- Technical success (primary endpoint)
- Procedure success (secondary endpoint)

The CEAC will classify relatedness of the above events to the Transcatheter Mitral Cerclage Annuloplasty procedure and to the cerclage device.

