## 5.0 STUDY DESIGN

### 5.1 OVERVIEW OF STUDY DESIGN

This is an early feasibility study (EFS) of the Transmural Systems Transcatheter Mitral Cerclage Annuloplasty device. It is a prospective, open-label, multi-center, investigator-initiated, and independently-adjudicated investigation of the cerclage device in patients with symptomatic functional mitral valve regurgitation due to underlying cardiomyopathy.

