#### **9.10 OFF STUDY CRITERIA**

- Completion of the 5-year follow-up
- The subject voluntarily withdraws
- The cerclage procedure fails and no implant is left behind, after the first 30 day assessment
- Significant subject non-compliance with follow-up visits, despite repeated site Principal Investigator effort to assure compliance including telephone encouragement and registered letter reminders if necessary.
- Death

Confirmation of survival will be sought from all subjects, even after they voluntarily withdraw, by contacting their physicians, the social security death index, and the subjects themselves.

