**11.2.1 Personal Identifiable Information**

Clinical data from subjects participating in this trial will retain personally identifiable information. This includes CT scans, echocardiograms, fluoroscopy, and medical records.

Abstracted data will be coded and de-identified for transmission to participating subcontracting investigators, such as core imaging laboratories, clinical events adjudication committee, and statistician.

DICOM data will be stored in a secured NIH research PACS system for analysis, including personally identifiable information.

See also section 13.3 (“subject confidentiality”).

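### Independent adjudication of deaths stops at one year, although relatedness of death is an endpoint with no stated horizon and safety follow-up runs to year 5

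*Combined protocol and SAP*

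**What the plan says.** Section 5.1 describes the study as an "independently-adjudicated investigation of the cerclage device". Section 9.6 sets the scope of that adjudication: "An independent Clinical Events Adjudication Committee will review all of the following that occur in the first year". The list has three items: deaths, technical success and procedural success. For these, "The CEAC will classify relatedness of the above events to the Transcatheter Mitral Cerclage Annuloplasty procedure and to the cerclage device".

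The endpoint reaches further, or at least is not bounded. Section 9.5 lists "Mortality, all-cause, cardiovascular vs non-cardiovascular, peri- vs non-periprocedural, including Transcatheter Mitral Cerclage Annuloplasty relatedness" among the exploratory endpoints and gives no horizon. The first off-study criterion in 9.10 is "Completion of the 5-year follow-up". The schedule in 5.4 has contacts at 2, 3, 4 and 5 years for vital status and serious events, and 10.2.3 continues SAE and SADE recording at annual visits after month 12. The version history shows that long-term event recording and reporting came in with Amendment G.

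Outside the committee's window the general rule in 9.2 applies: "Clinical events are classified by the site Principal Investigator and confirmed by the NIH Principal Investigator". Section 14.1 makes the NIH Principal Investigator the sponsor representative as well.

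**The concern.** The implant is permanent and stays under tension. Sections 10.1 and 11.2 name myocardial erosion, with perforation or tamponade, among the anticipated effects. A late death that might be due to the device is one of the main things that years 2 to 5 can show. Whether it counts as related is a judgement, and after year 1 the records may be thin, because 5.4 accepts a phone call and the primary physician's notes. That is where independence helps most, and where the plan withdraws it.

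At stake is the credibility of one exploratory safety result: the proportion of deaths attributed to the procedure or device. If first-year deaths are attributed by the committee and later ones by the investigators, a single table mixes two standards. The later part rests partly on a party with a stake in the answer.

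**Working it through.** **1. Who classifies relatedness of a death, and when**

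| Time of death | Classification under the protocol | Independent case review |
|---|---|---|
| Up to 12 months | Site investigator, confirmed by NIH Principal Investigator (9.2); committee classifies relatedness (9.6) | Yes |
| After 12 months, to year 5 | Site investigator, confirmed by NIH Principal Investigator (9.2) | None assigned |

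The other bodies do not fill the second row. Under 9.8 the DSMB reviews progress reports, and the IRB sees SAEs and SADEs at continuing review. The decision whether a death signals unreasonable risk belongs to the sponsor and the NIH Principal Investigator. None of these is told to classify relatedness case by case. Scheduled follow-up outside adjudication is (5 − 1)/5 = 80%.

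**2. What the limit does not touch**

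Technical success is measured on leaving the catheterization laboratory (9.3), procedural success at 30 days (9.4.1), and the stopping rule counts deaths within 30 days (9.9). All fall inside year 1.

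**3. Rough size of the gap (illustration only)**

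The protocol gives no expected mortality beyond 30 days, so there is no plan figure to reproduce. Inputs are the death rates that section 3.0 quotes from two randomized trials of edge-to-edge clip repair: 29.1% (device) and 46.1% (control) at 24 months in one, 24.3% (intervention) and 22.4% (control) at 12 months in the other. N = 30 comes from 9.1. Rates of 5% and 10% a year are added as assumed lower values.

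Assumptions: constant hazard, a population like those trials, and no loss to follow-up. With p the risk at t years, S(x) = (1 − p)^(x/t). Deaths up to year 1 = 30 × (1 − S(1)). Deaths in years 1 to 5 = 30 × (S(1) − S(5)). Share after year 1 = (S(1) − S(5))/(1 − S(5)).

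| Input | S(1) | S(5) | Deaths to year 1 | Deaths, years 1–5 | Share after year 1 |
|---|---|---|---|---|---|
| 29.1% at 24 months | 0.842 | 0.423 | 4.7 | 12.6 | 73% |
| 46.1% at 24 months | 0.734 | 0.213 | 8.0 | 15.6 | 66% |
| 24.3% at 12 months | 0.757 | 0.249 | 7.3 | 15.3 | 68% |
| 22.4% at 12 months | 0.776 | 0.281 | 6.7 | 14.8 | 69% |
| 5% a year (assumed) | 0.950 | 0.774 | 1.5 | 5.3 | 78% |
| 10% a year (assumed) | 0.900 | 0.590 | 3.0 | 9.3 | 76% |

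**4. Does the calendar allow five years for everyone?**

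The stated completion date is December 31, 2024. Amendment F is dated 2020-07-09, and section 1.0 contrasts new subjects with the first 10. Taking those 10 as the number treated by then, the other 30 − 10 = 20 have at most about 4.5 years. So the five-year counts in step 3 cannot all be observed by that date.

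The share after year 1 is less sensitive. With a common follow-up of T years it is (S(1) − S(T))/(1 − S(T)). At T = 3 the four quoted rates give 56% to 61%. At T = 2 they give 42% to 46%. Late deaths are the majority once follow-up reaches about three years and a large minority at two.

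**The case against.** The strongest reply is that this is a small, descriptive feasibility study with no acceptance criteria (9.1). The endpoint concerned is exploratory, and wherever 9.5 does give a horizon it ends by 12 months. Years 2 to 5 are deliberately light surveillance, so one-year adjudication may be a proportionate choice. Late deaths are not unseen: the DSMB and IRB continue, deaths appear in annual reports to the FDA and IRB (10.2.4), and necropsy is requested (5.4). Appendix A gives myocardial erosion a likelihood of 1, the lowest score it uses. This limits the weight of the point. It does not close the gap, because none of these routes classifies relatedness independently, and the endpoint as written does not stop at year 1.

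Four stronger readings are tempting, and the documents do not support them.

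- *The committee is anchored on the primary endpoint.* Section 9.3 says "The primary endpoint is classified by the NHLBI Principal Investigator and reviewed for possible reclassification by the Clinical Events Adjudication Committee", so the investigator does classify first. But the committee may reclassify, 9.6 has it classify relatedness itself, and nothing says whether it sees the investigator's answer beforehand. Most components of technical success are also hard facts at laboratory exit.
- *The committee works only from summaries.* This rests on "Abstracted data will be coded and de-identified for transmission to participating subcontracting investigators, such as core imaging laboratories, clinical events adjudication committee, and statistician". That is a privacy sentence, and it names the core imaging laboratories alongside the committee, although 9.7 has those laboratories analyse all imaging. It does not define the committee's dossier.
- *Some 17 to 24 of 30 subjects will die within five years.* The totals in step 3 for the four quoted rates run from 17.3 to 23.6 (4.7 + 12.6 and 8.0 + 15.6). They count deaths from any cause and assume complete five-year follow-up, which the completion date rules out. Subjects entered under Amendment F may also have milder regurgitation than those in the quoted trials.
- *Late attribution has no check at all.* The site investigator and the NIH Principal Investigator both classify, and the bodies above continue to oversee. What is missing is independent attribution of the individual death.

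**Conclusion.** The point holds in a limited form. The plan calls the study independently adjudicated, makes relatedness of death an endpoint without a horizon and collects deaths to year 5, yet ends committee review of deaths at month 12. After that, attribution rests with the site investigator and the sponsor's own representative. The textual gap, four of five scheduled follow-up years, needs no assumption about mortality. That the endpoint is meant to cover years 2 to 5 is an inference from the length of follow-up, and the plan should say so either way.

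The share of deaths affected is only indicative: 66% to 73% with five full years at the quoted rates, and 56% to 61% with three. It rests on constant hazards and on populations borrowed from other trials. The number of device-related deaths among them cannot be estimated from the documents. No confirmatory or stopping decision changes. This is an inexpensive improvement to the safety attribution and does not challenge the primary result.

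**What to change.** In 9.6, keep the one-year window for technical and procedural success, but have the existing committee review every death, with its relatedness to the procedure and to the device, through the end of each subject's follow-up, up to five years. In 9.5, state the same horizon for the mortality endpoint. In 9.2, add that for deaths the committee's relatedness classification is the one reported.

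The cost is a few extra case reviews a year, plus collection of whatever records exist for each late death (hospital notes, death certificate, necropsy if done). The second item is real work, because phone contact is otherwise acceptable after year 1. No new committee or study visit is needed.

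Optionally, the committee could classify the primary and secondary endpoints before seeing the investigator's classification, with disagreements reported. That is a refinement and does not correct a documented bias.
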